8.3 Endpoints

8.3.1 Primary Endpoint(s)

The primary objective will be measured by the primary endpoint of investigator-assessed ORR in each cohort. It is defined as the number of subjects with a best overall response (BOR) of confirmed CR or PR, according to RECIST 1.1 criteria, divided by the number of treated subjects in the related cohort. The final analysis of the primary endpoint will occur at least 6 months after the last enrolled subject's first dose of study therapy. The BOR is defined as the best response designation recorded between the date of first dose and the date of initial objectively documented progression per RECIST v1.1 or the date of subsequent therapy, whichever occurs first. For subjects without documented progression or subsequent therapy, all available response designations will contribute to the BOR determination. For purposes of analysis, if a subject receives one dose and discontinues the study without assessment or receives subsequent therapy prior to assessment, this subject will be counted in the denominator (as non-respondent.)

The investigator-assessed ORR will be further characterized by the investigator assessed duration of response (DOR) and rate of complete response (CR). DOR is defined as the time from first confirmed response (CR or PR) to the date of the first documented tumor progression as determined using RECIST 1.1 criteria or death due to any cause, whichever occurs first. For subjects who neither progress nor die, the DOR censoring will be the same as PFS censoring (see Section 8.3.3). In each cohort, DOR will be computed for subjects with a BOR of PR or CR.

8.3.2 Secondary Endpoint(s)

The secondary objective will be measured by the secondary endpoint of IRRC-assessed ORR in each cohort. It is defined as the number of subjects with a best overall response (BOR) of confirmed CR or PR, according to RECIST 1.1 criteria, divided by the number of treated subjects in the related cohort. The final analysis of the secondary endpoint will occur the time of the primary endpoint analysis. The BOR is defined as the best response designation recorded between the date of first dose and the date of initial objectively documented progression per RECIST v1.1 or the date of subsequent therapy, whichever occurs first. For subjects without documented progression or subsequent therapy, all available response designations will contribute to the BOR determination. For purposes of analysis, if a subject receives one dose and discontinues the study without assessment or receives subsequent therapy prior to assessment, this subject will be counted in the denominator (as non-respondent).

The IRRC-assessed ORR will be further characterized by the IRRC-assessed duration of response (DOR) and rate of CR. DOR is defined as the time from first confirmed response (CR or PR) to the date of the first documented tumor progression as determined using RECIST 1.1 criteria or death due to any cause, whichever occurs first. For subjects who neither progress nor die, the DOR censoring will be the same as PFS censoring (see Section 8.3.3). In each cohort, DOR will be computed for subjects with a BOR of PR or CR.

Investigator-assessed and IRRC-assessed DCR will be reported. Disease control rate (DCR) is defined as the number of subjects with a BOR of confirmed CR or PR or SD lasting at least 12 weeks divided by the number of treated subjects.

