3.1.9 Follow up

3.1.9.1 Follow -up for all Cohorts After Initial Study Treatment

Follow-up begins when the decision to discontinue a subject from study therapy is made (no further treatment with study therapy).

Subjects who started a systemic cancer treatment outside of this study will not continue with tumor imaging assessments.

Subjects who discontinue treatment for reasons other than tumor progression will continue to have tumor imaging assessments beginning 6 weeks (\pm 1 week) after first dose and continuing every 6 weeks (\pm 1 week) for the first 24 weeks from first dose, and every 12 weeks (\pm 1 week) thereafter until disease progression (investigator-assessed RECIST 1.1-defined progression).

In order to help reduce unnecessary participant burden and help optimize participant safety by reducing the possible radiation exposure risk of a secondary malignancy, investigators should reduce scan frequency for participants having disease control 3 years after the first dose per Table 5.1-14b. The participant's tumor assessment schedule should be modified to every 24 weeks, unless clinically indicated, to continue tumor assessments every 12 weeks.

- Subjects will be followed for drug-related toxicities until these toxicities resolve, return to baseline, or are deemed irreversible. All adverse events will be documented for a minimum of 100 days after last dose.
- After completion of the first two follow-up visits, subjects enrolled in the MSI-H cohort (Cohorts N and N+I) and Cohorts C3, C4, C5, and C6 will continue to survival follow-up per Table 5.1-7. Please see Section 3.1.10 for end of the study definition and duration of follow-up for survival.
- Refer to Table 5.1-7 for additional follow-up assessments.

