8.3.3 Exploratory Endpoint(s)

Exploratory safety objectives will include safety and tolerability of nivolumab monotherapy (mStage 1 and 2) or nivolumab in combination with ipilimumab (cStage 1 and 2 and the cohort C3) in subjects with metastatic MSI-H CRC, nivolumab in combination with anti-LAG-3 antibody (BMS-986016, Cohort C5) in subjects with metastatic dMMR/MSI-H mCRC, or nivolumab in combination with daratumumab (Cohort C6) in subjects with metastatic non-MSI-H (pMMR) mCRC, as measured by the incidence of adverse events and specific laboratory abnormalities (worst grade) in each treatment arm. In addition, the safety and tolerability of nivolumab in combination with ipilimumab in subjects with metastatic non-MSI-H CRC will also be evaluated. Toxicities will be graded using the National Cancer Institute (NCI) Common Terminology Criteria for Adverse Events (CTCAE) version 4.0.

Exploratory efficacy objectives will be measured by exploratory endpoints of PFS (using investigator and IRRC assessments) and OS in all treated subjects with metastatic CRC within each cohort. PFS is defined as the time from first dosing date to the date of the first documented progression, or death due to any cause, whichever occurs first. Subjects who die without a reported prior progression will be considered to have progressed on the date of their death. Subjects who did not progress or die will be censored on the date of their last evaluable tumor assessment. Subjects who did not have any on-study tumor imaging assessments and did not die will be censored on the first dosing date. Subjects who started any subsequent anti-cancer therapy without a prior reported progression, including death, will be censored at the last evaluable assessment prior to initiation of the subsequent anti-cancer therapy.

OS is defined as the time from first dosing date to the date of death. A subject who has not died will be censored at their last known date alive. OS will be followed continuously while subjects are on the study drug and every 3 months via in-person or phone contact after subjects discontinue the study drug.

The PK objective will be measured from serum concentration. Samples will be collected to characterize pharmacokinetics of nivolumab monotherapy, PK of nivolumab, ipilimumab, BMS-986016, and daratumumab when combined, and to explore exposure-response relationships (Section 5.5).

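### As worded, DOR censoring for a responder who starts new therapy before progression depends on whether that responder later dies, and Section 8.3.3 does not say which of its own two PFS sentences takes priority

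*Combined protocol and SAP*

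**What the plan says.** Four provisions of the protocol meet here.

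- **DOR event (Sections 8.3.1 and 8.3.2).** DOR runs from first confirmed response to "the date of the first documented tumor progression as determined using RECIST 1.1 criteria or death due to any cause, whichever occurs first". There is no cut-off at new therapy.
- **DOR censoring (same sections, same sentence in both).** "For subjects who neither progress nor die, the DOR censoring will be the same as PFS censoring (see Section 8.3.3"). DOR has no other rule for subsequent therapy.
- **PFS (Section 8.3.3).** One sentence reads "Subjects who started any subsequent anti-cancer therapy without a prior reported progression, including death, will be censored at the last evaluable assessment" before that therapy. Another reads "Subjects who die without a reported prior progression will be considered to have progressed on the date of their death". Nothing says which applies to a subject who switches therapy and then dies.
- **Best overall response (Sections 8.3.1 and 8.3.2).** For subjects with progression or new therapy, the window closes at "the date of initial objectively documented progression per RECIST v1.1 or the date of subsequent therapy, whichever occurs first". The responder set is thus defined with a cut-off at new therapy.

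Two follow-up rules decide what can be observed after a switch. Section 3.1.9.1 states "Subjects who started a systemic cancer treatment outside of this study will not continue with tumor imaging assessments". Section 8.3.3 continues survival contact "every 3 months via in-person or phone contact after subjects discontinue the study drug". Section 8.4.2.1 summarises DOR by Kaplan-Meier.

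**The concern.** Kaplan-Meier requires that being censored at a given time carries no information about what happens afterwards. Under the DOR sentence, two responders who switch on the same day are treated differently according to what happens later. The one who dies stays in the risk set until death and counts as an event. The one who survives is removed back at the last scan before the switch. Because scans stop after outside systemic therapy while survival contact goes on, death on another treatment is the main event still recordable for these subjects.

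The case is foreseeable. MSI-H subjects may stop treatment without progression, for toxicity or at maximum clinical benefit (Section 3.1.4.1). For the IRRC-assessed DOR, a responder may also switch after progression called by the investigator but not by the IRRC.

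At stake is how durable the responses appear. Section 1.1.8 says ORR is to be judged by its size and its duration, and DOR characterises both the primary and the secondary ORR. The re-initiation version of DOR is to be defined similarly (Section 8.3.3), so the wording would carry over.

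**Working it through.** The plan gives no figure for this point, so the check is of the rules first and then of their possible effect.

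**1. One subject under the text.** Assume response at month 3, last scan at month 8, new therapy at month 9, and either death at month 30 or alive at cut-off. DOR times are measured from response: 30 − 3 = 27 and 8 − 3 = 5.

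| Sentence governing in 8.3.3 | PFS, later dies | PFS, alive | DOR, later dies | DOR, alive |
|---|---|---|---|---|
| Subsequent therapy | censored at 8 | censored at 8 | event at 27 | censored at 5 |
| Death | event at 30 | censored at 8 | event at 27 | censored at 5 |

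In the first row PFS is consistent and DOR departs from it. In the second row the two agree, but both let later death decide whether the subject is censored. DOR is outcome-dependent in both rows.

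**2. Ten responders by hand.** S(t) is the product of (1 − d/n) over event times. Months are from response. Eight responders have events at 6, 12, 18 and 24 and censoring at 30, 36, 36 and 36. Two more switch at month 9 with a last scan at month 8; one dies at month 20 and the other stays alive.

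- Rule A, both switchers censored at 8: S(12) = 9/10 × 6/7 = 77.1%; S(24) = 77.1% × 5/6 × 4/5 = 51.4%.
- Rule B, as worded (event at 20; the other censored at 8): S(12) = 9/10 × 7/8 = 78.8%; S(24) = 78.8% × 6/7 × 5/6 × 4/5 = 45.0%.
- Rule C, switching ignored and both followed for death: S(12) = 9/10 × 8/9 = 80.0%; S(24) = 80.0% × 7/8 × 6/7 × 5/6 = 50.0%.

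B lies above A at 12 months and below both consistent rules at 24 months.

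**3. Simulation, switching unrelated to impending progression.** 200,000 responders per scenario, exponential times. The 12-week scan interval comes from Table 5.1-14a; every other input is an assumption: 24-month DOR of 50% or 75%, 5–20% switching by 24 months, 12-month mortality after the switch of 20% or 40%, and 36–60 months of follow-up. Differences are in percentage points over the 12 scenarios.

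| Difference | 24 months | 48 months |
|---|---|---|
| B − A, all scenarios | −0.2 to −5.3 | −0.9 to −13.7 |
| B − A, 5–10% switching | −0.2 to −2.6 | −0.9 to −6.8 |
| B − C, all scenarios | −0.1 to −2.3 | −0.6 to −7.0 |

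The smallest B − A difference at 24 months is 52.4% against 52.6%; the largest is 71.2% against 76.5%.

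A harsher set of assumptions has a true median DOR of 24 months, all switching 2–12 months after response, a median of 12 months' survival afterwards, and cut-off 24–48 months after response. With 8%, 16% and 25% switching, the 24-month rate is 47%, 45% and 42% as worded, against 49–50% under rule A (truth 50%). Varying survival after the switch from 6 to 30 months widens the shortfall to about 1 to 11 points.

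**4. Simulation, switching shortly before progression would have been documented.** Median DOR, cut-off and survival after the switch are as in the harsher set, with a median lead of 3 months. With about 5%, 10% and 16% switching, the 24-month rate is 51%, 52% and 54% as worded and 52%, 55% and 57% under rule A (truth 50%). Rule B is again below rule A, but here rule A is further from the truth, on the optimistic side.

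**The case against.** The strongest reply is that the sentence is loose shorthand. Neither progressing nor dying is a common way of saying without an event, and the sentence goes on to equate DOR censoring with PFS censoring, so alignment was probably intended. That is likely, but the sentence does not say it, and a programmer following it literally would produce rule B.

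A reader might infer that DOR flatly contradicts PFS. The documents do not go that far. Section 8.3.3 also counts deaths without reported prior progression on the date of death, and no priority is given. If that sentence governs, the two endpoints agree, but PFS then has the same outcome dependence. The defect moves; it does not disappear.

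A reader might also infer that the wording biases DOR by a known amount in a known direction. That is not supported either. The documents give no rate of switching before progression, and step 4 shows that the consistent rule can itself be optimistic if switching anticipates progression.

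Precision matters too. With 20 responders (the Simon rejection boundary is 20 of 48), the standard error of a 50% rate is √(0.5 × 0.5 / 20) = 11 points before any censoring, larger than most of the shifts above.

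Finally, the protocol refers to a SAP for other definitions (Sections 8.3.3, 8.4.5 and 8.4.7.2). Its text was not among the material reviewed, so it may already settle the point.

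**Conclusion.** The concern stands as a defect of wording with a real analytical consequence. Read literally, the DOR rule makes censoring depend on later death, it conflicts with the subsequent-therapy sentence for PFS, and neither possible priority within Section 8.3.3 removes the outcome dependence.

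The size cannot be settled from the documents. Relative to a rule that censors every switcher, the wording gave a lower 24-month rate in every simulation: from 0.2 points to several points, and under 3 points in the first set with 5–10% switching. The gap grew by 48 months. Early in a small sample it can run the other way, as the ten-responder example shows at 12 months. Whether the result as worded lies below or above the truth depends on why responders switch.

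It would be wrong to infer that the primary result is affected. DOR is descriptive; the ORR definition, the Simon stopping and rejection rules and the precision tables for Cohorts C3, C5 and C6 do not use it. The correction should still be made, because it brings DOR into line with a cut-off at new therapy that the protocol already applies to best overall response and states for PFS.

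**What to change.** In Section 8.3.3, state that a subject who starts subsequent anti-cancer therapy with no progression or death before that therapy is censored at the last evaluable assessment before it, regardless of later progression or death. This settles the priority between the two PFS sentences.

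In Sections 8.3.1 and 8.3.2, replace the censoring sentence with a statement that DOR uses the same event and censoring rules as PFS for all responders, timed from first confirmed response. Editing only these two sections would leave the PFS ambiguity in place.

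The cost is a sentence in each of three sections and the matching programming; no new data are needed. The downside is that some late deaths after new therapy no longer count as DOR events, and if responders switch because progression is near, the resulting curve can be optimistic. Reporting the number of responders censored for new therapy beside the curve would let readers judge that.

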8.3.3 Exploratory Endpoint(s)

Exploratory safety objectives will include safety and tolerability of nivolumab monotherapy (mStage 1 and 2) or nivolumab in combination with ipilimumab (cStage 1 and 2 and the cohort C3) in subjects with metastatic MSI-H CRC, nivolumab in combination with anti-LAG-3 antibody (BMS-986016, Cohort C5) in subjects with metastatic dMMR/MSI-H mCRC, or nivolumab in combination with daratumumab (Cohort C6) in subjects with metastatic non-MSI-H (pMMR) mCRC, as measured by the incidence of adverse events and specific laboratory abnormalities (worst grade) in each treatment arm. In addition, the safety and tolerability of nivolumab in combination with ipilimumab in subjects with metastatic non-MSI-H CRC will also be evaluated. Toxicities will be graded using the National Cancer Institute (NCI) Common Terminology Criteria for Adverse Events (CTCAE) version 4.0.

Exploratory efficacy objectives will be measured by exploratory endpoints of PFS (using investigator and IRRC assessments) and OS in all treated subjects with metastatic CRC within each cohort. PFS is defined as the time from first dosing date to the date of the first documented progression, or death due to any cause, whichever occurs first. Subjects who die without a reported prior progression will be considered to have progressed on the date of their death. Subjects who did not progress or die will be censored on the date of their last evaluable tumor assessment. Subjects who did not have any on-study tumor imaging assessments and did not die will be censored on the first dosing date. Subjects who started any subsequent anti-cancer therapy without a prior reported progression, including death, will be censored at the last evaluable assessment prior to initiation of the subsequent anti-cancer therapy.

OS is defined as the time from first dosing date to the date of death. A subject who has not died will be censored at their last known date alive. OS will be followed continuously while subjects are on the study drug and every 3 months via in-person or phone contact after subjects discontinue the study drug.

The PK objective will be measured from serum concentration. Samples will be collected to characterize pharmacokinetics of nivolumab monotherapy, PK of nivolumab, ipilimumab, BMS-986016, and daratumumab when combined, and to explore exposure-response relationships (Section 5.5).

The discordance rate between repeat MSI testing and prior MSI testing will be characterized using test results from both MSI-H and non-MSI-H cohorts (mStage1/2 and cStage1/2).

Other exploratory endpoints for immunogenicity, pharmacogenomics, and outcomes research are discussed in detail in Sections 5.5, 5.6, and 5.7, respectively.

For the evaluation of clinical activity of nivolumab monotherapy or combination treatment reinitiation, new endpoints will be considered: BOR-re-initiation (BOR-R), ORR-re-initiation (ORR-R), DCR-re-initiation (DCR-R), TTR-re-initiation (TTR-R), DOR-re-initiation (DOR-R), PFS-re-initiation (PFS-R) and OS-re-initiation (OS-R). These endpoints will be defined similarly as the original ones but using the new re-initiation start date or new baseline evaluations as reference, where apply. Detailed definition of these endpoints will be provided in the SAP.

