- 5. Subjects with a condition requiring systemic treatment with either corticosteroids (> 10 mg daily prednisone equivalents) or other immunosuppressive medications within 14 days of study drug administration. Inhaled or topical steroids and adrenal replacement doses > 10 mg daily prednisone equivalents are permitted in the absence of active autoimmune disease.

Re-initiation of Treatment for MSI-H Cohorts

Subjects in MSI-H cohorts who discontinue study treatment at Maximal Clinical Benefit, (Section 3.1.4.1) are permitted to re-initiate treatment, if disease progression defined by RECIST criteria occurs within 1 year (≤52 weeks) and protocol-defined criteria (Section 4.3.9) are met.

Study Assessments: The primary endpoint of this study is ORR which is based on tumor assessments at baseline and then at 6 weeks from first dose which continue every 6 weeks for the first 24 weeks and every 12 weeks thereafter until disease progression (investigator-assessed RECIST 1.1-defined progression) or treatment discontinuation, whichever occurs later.

Statistical Considerations:

Sample Size: This study will consist of 5 cohorts: non-MSI-H safety cohort, MSI-H cohort (Cohort N and Cohort N+I), Cohort C3 (MSI-H subjects who have not had prior therapy for their metastatic disease), MSI-H Cohort C5 Cohort and non-MSI-H Cohort C6. It is expected to treat up to approximately 96 central-pathology-lab-confirmed subjects (up to 29 non-MSI-H and up to 67 MSI-H) for the initial non-MSI-H and MSI-H cohorts. It is expected to treat approximately 30 subjects in cohort C3. It is expected to treat approximately 40 MSI-H subjects in C5 Cohort and 40 non-MSI-H subjects C6 Cohort.

Sample size determination for non-MSI-H and MSI-H cohorts:

The MSI-H cohort will include subjects who are defined as MSI-H based on standard diagnostic testing documented in the subject's medical history and prospectively confirmed in the current study by repeat testing using a polymerase chain reaction (PCR) test.

The non-MSI-H safety cohort will include all subjects testing non-MSI-H by the repeat PCR test, including those who were MSI-H by medical history but not confirmed by repeat testing.

For the non-MSI-H safety cohort, sample size is not based on power considerations and will depend on the observed toxicity.

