All subjects will undergo screening evaluations to determine eligibility within 28 days prior to the start of therapy. A baseline tumor imaging assessment will be performed prior to the start of therapy. Tumor tissue must be provided for biomarker analysis. Central lab must provide IVRS with confirmation of receipt of evaluable tumor tissue prior to study treatment. Subjects whose repeat testing does not confirm MSI-H status will be replaced but will be allowed to continue on study therapy. Subjects on C3 will be accepted with a valid local MSI result.

Treatment beyond initial investigator-assessed progression is permitted if the subject has an investigator-assessed clinical benefit and is tolerating study drug, see Section 4.3.8. The investigator-assessed tumor response based on RECIST 1.1 criteria will be used to guide the stage 1 decision and for the primary analysis of the ORR. In addition, an independent radiology review

Protocol Amendment No: 09

Approved v1000 930073805 10.0

committee (IRRC) will perform central review of the imaging per RECIST 1.1 criteria upon study completion. Details will be included in the IRRC charter.

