Survival Status		X	Every 3 months after F-U 2 (R); may be accomplished by visit, phone contact or email, to assess subsequent anti-cancer therapy for a minimum of 5 years, in all cohorts. (Please see Section 3.1.10 for end of the study definition.)		

Subjects must be followed for at least 100 days after last dose of study therapy. Follow-up visit #1 after re-initiation (FU1 R) occurs approximately 35 days (± 7 days) after last dose or coinciding with the date of discontinuation (± 7 days) if date of discontinuation is greater than 35 days after last dose. Follow up after re-initiation visit #2 (FU2 R) occurs approximately 80 days (± 7 days) after FU1 (R).

Table 5.1-14a: Standard Tumor Imaging Assessment

Tumor imaging assessments will occur every 6 weeks from the date of first dose (\pm 1 week) for the first 24 weeks, then every 12 weeks (\pm 1 week) thereafter until disease progression or treatment is discontinued (whichever occurs later).

Table 5.1-14b: Reduced Tumor Imaging Assessment

All Subjects (Except Re-initiation Subjects)	Re-initiation Subjects
Scans every 12 weeks (\pm 1 week) for 3 years after first dose, then every 24 weeks (\pm 2 weeks) thereafter*	Scans every 12 weeks (\pm 1 week) for 3 years after first dose following reinitiation, then every 24 weeks (\pm 2 weeks) thereafter ^a

 $^{^{\}mathrm{a}}$ Scans may continue every 12 weeks (\pm 1 week) if clinically indicated.

Notes: CT or MRI chest, abdomen, pelvis and all known sites of disease. Use same imaging method as was used at screening/baseline.

Subjects with a history of brain metastasis may have surveillance MRI approximately every 12 weeks from the date of first dose, or sooner if clinically indicated.

Protocol Amendment No: 09

b Survival visits = every 3 months from FU2 (R). Survival visits will be conducted for all MSI-H subjects who have re-initiated treatment.

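### IRRC-assessed DOR and PFS censor subjects whose scheduled imaging ended at investigator-called progression, so both are expected to read somewhat long

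*Combined protocol and SAP*

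**What the plan says.** **When imaging stops.** Table 5.1-14a schedules scans "until disease progression or treatment is discontinued (whichever occurs later"). The Synopsis (Study Assessments) makes clear that the investigator's call is the one that counts: "until disease progression (investigator-assessed RECIST 1.1-defined progression) or treatment discontinuation, whichever occurs later". Off treatment, section 3.1.9.1 reads: "Subjects who discontinue treatment for reasons other than tumor progression will continue to have tumor imaging assessments beginning 6 weeks", and those scans run "thereafter until disease progression (investigator-assessed RECIST 1.1-defined progression"). The same section adds: "Subjects who started a systemic cancer treatment outside of this study will not continue with tumor imaging assessments". So a subject taken off treatment at investigator-assessed progression (PD) has no further scheduled scans.

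**When the IRRC reads.** Section 3.1 states that the independent radiology review "committee (IRRC) will perform central review of the imaging per RECIST 1.1 criteria upon study completion". Section 8.3.2 places the IRRC analysis at the time of the primary endpoint analysis. Either way, no central read precedes the end of imaging, and section 5.4 does not require confirmation of PD.

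**How the IRRC endpoints censor.** For PFS, by investigator and by IRRC, section 8.3.3 says "Subjects who did not progress or die will be censored on the date of their last evaluable tumor assessment". Subjects who start new anti-cancer therapy without prior PD are censored at the last evaluable scan before it. For IRRC-assessed DOR, section 8.3.2 says "For subjects who neither progress nor die, the DOR censoring will be the same as PFS censoring". Sections 8.4.2.2 and 8.4.2.3 summarise both by Kaplan-Meier and name no supplementary analysis.

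**The concern.** Take a subject whose investigator calls PD and stops treatment, while the IRRC, on the same scans, does not call PD. Scheduled imaging is over, so unless an extra scan exists, a later IRRC progression will not be seen. The censoring rule then treats the subject as leaving at average risk. Both readers apply RECIST 1.1 to the same images, so a subject the investigator has just called progressed is plausibly closer to IRRC progression than the others still at risk. Kaplan-Meier would redistribute that subject's weight to people who are doing better.

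At stake is how durability is described. In an open-label, single-arm study the independent read is the natural check on the investigator's, and IRRC DOR is what characterises the secondary endpoint.

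**Working it through.** The plan states no median, event count or discordance rate for IRRC DOR or PFS, so there is no figure to reproduce. The size below is illustrative.

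**Inputs.** From section 8.1: n = 48 per arm and a target response rate of 52%, hence 0.52 × 48 ≈ 25 responders (24 used). Assumed, not in the documents:
- investigator PD time T is exponential with a 12-month median, so λ = ln 2/12 = 0.0578 per month;
- a share d = 10%, 20% or 30% of subjects is discordant, and their IRRC PD follows after an exponential lag L with mean 3 months (μ = 1/3);
- either all or half of the discordant subjects stop imaging at T;
- there are no deaths, and the same model serves DOR.

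**Step 1: IRRC progression-free proportion at 12 months with complete imaging.** This is (1−d) × 0.5 + d × P, where P = Pr(T+L > 12) = [μe^(−12λ) − λe^(−12μ)]/(μ−λ) = [0.3333 × 0.5 − 0.0578 × 0.0183]/0.2756 = 0.601. The results are 0.510, 0.520 and 0.530.

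**Step 2: what Kaplan-Meier estimates if all discordant subjects are censored at T.** The observed hazard is (1−d)λ, so the estimate tends to 0.5^(1−d): 0.536, 0.574 and 0.616.

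**Step 3: standard error (Greenwood).** SE = KM × √[(1−d)(e^(12λ) − 1)/n] = KM × √[(1−d)/n], because e^(12λ) = 2. For d = 20% and n = 48: 0.574 × √(0.8/48) = 0.074. For n = 24, multiply by √2.

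**Step 4: half continue imaging.** With S and S_L the survival functions of T and T+L, and f_L the density of T+L, the observed hazard is [(1−d)λS + (d/2)f_L] / [(1−d/2)S + (d/2)S_L]. Integrating to 12 months gives KM 0.523, 0.546 and 0.570.

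| d | Complete imaging | KM, all stop | Bias/SE, n=48 | Bias/SE, n=24 | KM, half stop | Bias/SE, n=48 | Bias/SE, n=24 |
|---|---|---|---|---|---|---|---|
| 10% | 0.510 | 0.536 | 0.35 | 0.25 | 0.523 | 0.17 | 0.12 |
| 20% | 0.520 | 0.574 | 0.73 | 0.52 | 0.546 | 0.35 | 0.25 |
| 30% | 0.530 | 0.616 | 1.15 | 0.81 | 0.570 | 0.54 | 0.39 |

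Simulation of the same model agrees within simulation error (n = 48, all stop: up to 1.2 SE at 30%).

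**Step 5: a second model on the protocol's scan calendar** (every 6 weeks to week 24, then every 12 weeks). IRRC median is 52 weeks, and discordant subjects are called by the investigator one scan early. Complete imaging gives 52.7% at 52 weeks. With all stopping, the censored estimate is 55.6%, 58.6% and 61.9% at 10%, 20% and 30% discordance. With half stopping it is 54.1%, 55.6% and 57.2%.

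**Step 6: is the direction forced?** No. If investigator PD is made independent of later IRRC PD, the bias in the second model is within 0.2 points of zero.

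**Step 7: does counting investigator PD as an event help?** At 20% discordance in the second model it gives 51.2%, against 52.7% complete and 58.6% censored. In the first model with all stopping it gives 50.0%, against 51.0-53.0% complete and 53.6-61.6% censored. The pair brackets the complete-imaging value in both.

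**The case against.** Several features of the plan work against the bias.
- Treatment beyond progression is permitted (3.1.6, 4.3.8), with scans at least every 12 weeks, so some discordant subjects stay under observation.
- Section 5.3.1 requires unscheduled and outside scans that may show progression to be collected and sent for central review. It does not help once new therapy has begun, because 8.3.3 censors before it.
- Deaths without reported PD or new therapy count as events. They are dated at death, though, possibly later than IRRC PD would have been.
- Section 4.3.8 notes that a minority of subjects benefit despite initial PD, so not every investigator call heralds an IRRC call.

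All of this stands and reduces the expected size. None of it removes the problem for a subject who stops treatment at investigator PD and has no later usable scan.

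It can also be said that investigator-assessed DOR and PFS are already planned and count every investigator PD. That is a partial safeguard. It does not replace the proposed analysis, because it changes the set of responders and every PD date, not only the affected ones.

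Finally, censoring at the last evaluable scan is conventional, no decision rests on these curves, and the protocol defers some detail to a separate SAP (8.3.3, 8.4.5, 8.4.7.2) that was not available for review. A supplementary analysis could be there. What can be said is that sections 8.3 and 8.4 contain none and do not defer this censoring.

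**Conclusion.** The concern holds in limited form. IRRC-assessed DOR and PFS are expected to be biased upward, on condition that investigator PD predicts near-term IRRC PD. Under the assumed 10-30% discordance, the 12-month bias for DOR in about 24 responders is roughly 0.25-0.8 SE if every discordant subject stops imaging and 0.1-0.4 SE if half continue. For PFS in 48 subjects it is roughly 0.35-1.2 SE and 0.2-0.55 SE. Discordance, lag, median and share stopping are all assumptions. With low discordance the effect is negligible.

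A reader might infer that the IRRC curves are certainly inflated, that IRRC progression can never be observed after an investigator call, or that the independent confirmation of efficacy is undermined. The documents do not support this. The direction rests on a presumption, continued and extra scans exist for some subjects, and deaths are counted. The primary endpoint (investigator ORR), the 7/19 and 20/48 response gates and IRRC ORR are response counts that this censoring does not touch. The point concerns one measure supporting the secondary endpoint and one exploratory endpoint.

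**What to change.** In sections 8.3.2, 8.3.3 and 8.4.2.2, pre-specify a supplementary Kaplan-Meier analysis of IRRC-assessed DOR and PFS. It counts an event on the investigator PD date for any subject with no IRRC PD and no later evaluable scan before new therapy. Written this way, it also re-dates later deaths among such subjects to the investigator call.

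Report it beside the censored analysis for each cohort, give the number of subjects affected, and treat the two as an approximate range when describing durability. If a separate SAP already contains this, a cross-reference from section 8 is enough.

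Cost: wording in three sections and one extra Kaplan-Meier analysis of each endpoint per cohort, from data already collected. The IRRC median in the added analysis will be somewhat shorter.
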